PHI	Protected Health Information
PTSD	Post-Traumatic Stress Disorder
rTMS	Repetitive Transcranial Magnetic Stimulation
SCID-5	Structured Clinical Interview for DSM-5
SITBI	Self-Injurious Thoughts and Behavior Interview
TBS	Theta Burst Stimulation
TMS	Transcranial Magnetic Stimulation
TMT	Trails Making Test
TMT-B	Trails Making Test part B
TRD	Treatment Resistant Depression
UDS	Urine Drug Screen
UNC	University of North Carolina

Protocol Synopsis

Study Title	Open Label Study of the Efficacy, Durability, Safety and Feasibility of Intermittent Theta Burst Stimulation (iTBS) in Adolescents with Major Depressive Disorder: Effect Duration, Suicidality, and Non-Suicidal Self Injurious Behavior
Funder	Center for Health Innovation Grant- UNC Health
Clinical Phase	Pilot feasibility, open label
Study Rationale	
MDD (Major Depressive Disorder) is prevalent in the adolescent population and is associated with significant morbidity and in extreme cases mortality. Current treatment consists of medications, psychotherapy and ECT (Electroconvulsive Therapy), each having its own potential complications and rates of efficacy.
 
An alternative avenue of treatment is TMS (Transcranial Magnetic Stimulation), which has been FDA (Food and Drug Administration) approved in the treatment of adults, with evidence of efficacy and safety in adolescents. Current TMS treatments consist of a high burden of time – 37 minute daily treatments for 30 treatments. A potential solution to this is iTBS (Intermittent Theta Burst Stimulation), which cuts down the treatment time to 3 minutes per day. iTBS has been shown to be effective in adults, is non-inferior to prior FDA approved TMS protocols, and is itself FDA approved for treatment resistant MDD in adults.
 
Our study proposes to investigate the efficacy, durability, safety and feasibility of iTBS in adolescents with MDD.

Study Objective(s)	
 • To assess the efficacy in reducing depressive symptoms, durability of antidepressant effect, safety of treatment and feasibility of iTBS in 5 adolescents with MDD.
Test Article(s) (If Applicable)	Theta burst transcranial magnetic stimulation will be performed for the treatment of depression in adolescents.
Study Design	Open label, feasibility
Subject Population	Inclusion Criteria
key criteria for Inclusion and Exclusion:	
1. Subjects aged 13-17
 
2. Major Depressive Disorder (MDD) or Treatment Resistant Depression (TRD) by a score of >17 on Hamilton Depression Rating Scale (HAM-D) and >40 on Children's Depression Rating Scale Revised (CDRS-R)
 
Exclusion Criteria
 
1. Subjects with metallic implants, brain injury, seizure disorder
 
2. Current or lifetime history of an eating disorder, psychosis, bipolar disorder, substance abuse

	
3. Current inpatient psychiatric hospitalization, or current symptoms (including suicide ideation) that would require inpatient hospitalization
 
4. Pregnancy for female subjects
 
5. Any other condition investigators deem may interfere with study participation or safety

Number Of Subjects	5
Study Duration	
Participation will last 17 weeks. Treatment will occur 5 days a week for 4 weeks. 3 Follow-up visits will be performed.
 
Study will recruit for 1 year.

Study Phases	(1) Screening : screening for eligibility and obtaining consent
Screening	(2) Intervention : subjects will receive iTBS, 5 days a week for 4 weeks
Study Treatment	(3) Follow up : a follow up visit will be done at 1 week, 4 weeks, and 12 weeks after the last treatment session.
Follow-Up	
Efficacy Evaluations	Evaluations of CDRS-R (Children's Depressive Rating Scale Revised) and HAM-D (Hamilton Depression rating scale) scores will be used to measure efficacy. MMSE, Trails B, list generation, Columbia Suicide Scale, semi-structured interviews for Non-suicidal Self Injurious Behavior (NSSIB), and medical review will be used to evaluate safety. Assessment of the number and per cent treatments completed and number and percent of subjects who withdraw from treatment will be used to assess feasibility
Pharmacokinetic Evaluations	N/A
Safety Evaluations	
 Evaluations of CDRS-R (Children's Depressive Rating Scale Revised) and HAM-D (Hamilton Depression rating scale) scores will be used to measure efficacy. MMSE, Trails B, list generation, Columbia Suicide Scale, semi-structured interviews for Non-suicidal Self Injurious Behavior (NSSIB), and medical review will be used to evaluate safety. Assessment of the number and per cent treatments completed and number and percent of subjects who withdraw from treatment will be used to assess feasibility In addition, a medical review of symptoms, vital signs, UDS (Urine Drug Screen), physical exam, and applicable pregnancy test, regular assessment of adverse events and change in pregnancy status will be obtained.
Statistical And Analytic Plan	
This is a pilot feasibility study, and it will not be powered to show significance.
 
 We will compare pre- and post-treatment measures of depression in all subjects with repeated ANOVA measures Cognitive scales and safety assessments Descriptive statistics Pearson's r coefficient for correlation between Non-suicidal Self Injurious Behavior (NSSIB), depression, and suicidality changes

throughout the study.

- *The study may provide important preliminary data for NIH R01 applications.*

Data And Safety Monitoring Plan	PI is responsible for data quality management and ongoing assessment of safety
----------------------------------------	--------------------------------------------------------------------------------

1.0 BACKGROUND AND RATIONALE

1.1 Introduction

Major depression disorder (MDD) in adolescents is a very common neuropsychiatric disorder. [1] Left untreated, adolescent MDD can severely affect relationships, the ability to participate in extracurricular activities, academics, as well as social functioning.[1,2] In adolescents with MDD left untreated, the condition can affect the cognitive and emotional trajectory towards adulthood. In the worst-case scenario, adolescent MDD can lead to suicide. [1,2]

Current psychiatric treatment options for adolescent MDD include psychotherapy, medications and ECT. [3] While effective, there are limitations for those requiring more rapid stabilization or with limited access to trained therapists in their community. Psychotropic medications for adolescent MDD are typically offered as first line treatment for teens with severe symptoms. [3] Side effects and concern about increased suicidality limit the acceptance of medication by teens and their parents. ECT is effective; however, it is associated with significant adverse effects (anesthesia complications, memory deficits, and headache, nausea and vomiting, memory deficits). The effect of ECT on the developing adolescent brain is unknown, rendering ECT a less desirable treatment choice in this population. [4a] Close to 30-40% of adolescents do not respond to the first round of accepted treatment strategies including antidepressants and psychotherapy. [4b] Of these patients, only half will then respond to a second treatment strategy, including a change in antidepressant. [5] Those that do not respond to two standard treatment regimens may be considered as having "Treatment Resistant Depression (TRD)" [5].

Transcranial Magnetic Stimulation (TMS) is an effective [6-8] and FDA approved treatment for MDD in adults. However, a newer form of TMS — Intermittent Theta burst stimulation (iTBS) — has been developed [9, 10] and was recently FDA approved for MDD in adults [11] after it was shown to be non-inferior to conventional TMS in adults. iTBS sessions are much shorter in duration (3 minutes) than conventional TMS (37 minutes). The brevity of iTBS may allow for increased capacity, decreased cost, decreased treatment burden, and more accessibility of TMS for patients with MDD. [11] There is evidence that conventional TMS is safe and effective in adolescents. [12] Only a very small number of adolescents in just a few studies have been treated with iTBS. [13] Preliminary findings suggest safety and efficacy. [13,14]

It follows that determining whether Intermittent Theta Burst TMS is safe and effective in adolescents is an important question to answer. An open label, uncontrolled trial for the use of iTBS in 5 adolescents from age 13 to <18 with MDD will be performed, based on the relatively novel nature and the current availability of resources.

The rationale behind managing MDD in adolescents with a treatment modality used in adults may be explained by the significant symptoms overlap. The clinical presentation of MDD is similar in adolescents and adults save a few general differences. Both are marked by a low mood or loss of interest in enjoyable activities (anhedonia), along with a number of associated symptoms including a disruption of sleep and appetite, low energy, feelings of guilt, trouble with concentration, and at times suicide ideation. Differences found in the literature include a greater tendency for adolescents who are depressed to have so-called vegetative

symptoms (weight and appetite changes); while in adults, there is a greater tendency to have more concentration problems and anhedonia. [15] Diagnostic criteria also does not show difference between adolescents and adults for Major Depressive Disorder according to the current Diagnostic and Statistical Manual for Mental Disorders (DSM-V) except for clarification that in adolescents irritability can be present instead of or in addition to low mood. [16] Although there may be differences between the etiology of adolescent and adult MDD [15], there is precedence for managing adolescent MDD and adult MDD with similar modalities – various antidepressants such as fluoxetine or sertraline were initially studied in adults and later were studied and FDA approved in adolescents. Indeed, many of the practice parameters for managing adolescent MDD are based on the few large studies in adolescents, but also on adult studies and practical experience. [17]

Adolescence itself is a dynamic period both physiologically and psychologically. Around the start of puberty, there will start to be an increase in myelination in the brain, neural circuitry development, changes in the architecture of the gray and white matter in various regions of the brain, in addition to hormonal and neurotransmitter changes. [18] The onset of puberty depends on various factors including hereditary and environmental factors. [18] There are no differences in the DSM-V diagnostic criteria for MDD between the various stages of puberty, or between the various ages of adolescence. Fluoxetine has been FDA approved for pediatric MDD from age 8 to 17. [19] It is the authors' opinion that a study focusing on age 13 to 17 may serve to keep consistent the psychosocial factors of being in high school.

Although iTBS is FDA approved for TRD in adults, we will not focus exclusively on adolescents with TRD in this study, although they will be included. Optimization of two separate treatment strategies can take up to 3-4 months each, which will lead to prolonged suffering and may worsen the depression. The availability of an alternate and potentially effective treatment method may be welcomed by families. Some adolescents with MDD that are seen in our clinic cannot take part in routine treatment strategies due to logistic or financial reasons or due to the unavailability of resources – it is the goal of the investigators to not be biased against including these patients in the study. Due to the available resources for this study, the relative scarcity of adolescents with TRD may prolong recruitment. As a pilot study, the goal is to eventually perform a larger study, where exploring iTBS' place in the treatment algorithm for adolescents with MDD would be more appropriate.

1.2 Name and Description of Investigational Product or Intervention

TMS is currently an FDA approved treatment for MDD in adults who currently are in a depressive episode and have not responded to, or are unable to tolerate at least two medication trials. [20] Multiple devices have been approved by the FDA to provide TMS for MDD. [21] It is thus the aim of the researchers to study the treatment modality, and not the machine. The specific machine that we will be using is from MagVenture, and the specific model is the MagPro. The MagVenture machine that we intend to use is currently being used in our outpatient clinic to provide treatment. This machine has the capability to provide iTBS. The researchers that will be providing the TMS treatment have been trained in the use of this machine, and have logged multiple patient hours with this specific machine.

TMS treatment for MDD consists of delivering non-invasive, magnetic stimulation to the left prefrontal cortex, where it induces an electrical current, which in turn affects neuronal activity. [22] Repetitive stimulation

patterns of the prefrontal cortex at 10Hz for 40 minutes a day, five days a week, for 4-6 weeks, has been shown to improve depressive symptoms. [20] Theta Burst Stimulation (TBS) is a newer form of TMS. Instead of providing 10HZ stimulation, its stimulation pattern mimics endogenous brain theta rhythms. Studies of this form of stimulation have revealed improved induction of synaptic long-term potentiation, and have shown a benefit over placebo for treating MDD in adults, and have also been shown to be non-inferior to 10Hz TMS for the treatment of MDD in adults. [11]

A non-significant risk determination has been made and a request for this to be reviewed will be sent to the local IRB (Institutional Review Board). A device description will also be sent to the IRB for review. iTBS has also been FDA approved for adults.

iTMS (Intermittent Transcranial Magnetic Stimulation) (sec 12.2) and iTBS (the subject of this investigation) are interchangeable. rTMS (Repetitive transcranial magnetic stimulation) – is a general term that describes how a pulsed magnetic field is applied repeatedly, resulting in an electric current in the cerebral cortex. A TMS device uses a computer to drive an electromagnet to deliver a pulsed magnet field pattern known as the TMS protocol. The first TMS protocol that was FDA approved in 2008 delivered magnetic pulses at 10 cycles per second for 4 seconds followed by 26 seconds rest, repeated 75 times for a total of 3000 pulses delivered over 37.5 minutes. Theta burst stimulation (TBS) describes a new and different TMS protocol recently approved by the FDA in 2019. Theta burst TMS applies stimulation that resembles the endogenous EEG (electroencephalogram) theta rhythms observed in EEG measures of humans. Theta burst TMS protocols can be delivered continuously which is called continuous theta burst stimulation (cTBS), or intermittently which is called intermittent theta burst stimulation (iTBS). Clinical research has demonstrated that iTBS is effective for treatment of depression in adults, whereas cTBS is not effective. The efficacy data of a new iTBS was so impressive that it was FDA approved. This particular TMS protocol delivers the magnetic field in triplet bursts (three stimulations very close together at a frequency of 50 hz very quickly). The triplet bursts are repeated at a rate of 5 Hz for 2 seconds (30 pulses), followed by 8 seconds rest, repeated 20 times for a total of 600 pulses. This new FDA approved iTBS protocol is likely to be effective in adolescents with MDD.

In this study we will investigate the **efficacy and durability** of the effects of iTBS in adolescent depression (see Specific AIM 1 below) by measuring changes in clinical ratings [CDRS-R, HAM-D, and Non-suicidal Self Injurious Behavior (NSSIB) evaluations] before and after 4 weeks of treatment, as well as 12 weeks following treatment. We expect that subjects will show: improvement in symptoms over 20 iTBS sessions as measured by the Children's Depression Rating Scale Revised (CDRS-R), HAM-D and Non-suicidal Self Injurious Behavior (NSSIB) measures, and persistence of this reduction of depressive symptoms through the 12 weeks follow up period of the study. In this study, we will investigate the **safety** of the effects of iTBS in adolescent depression (see Specific Aim 2 below). We will investigate safety of the treatment regimen by assessing suicidality. We expect suicidal thoughts and behavior will reduce with iTBS treatment as measured by the Columbia Suicide Severity Rating Scale (C-SSRS) and a psychiatrist's clinical assessment. We also expect that those with NSSIB at the start of the trial will have less after iTBS treatments. We do not expect any change in cognition measured with MMSE, Trails B, and list generation. We will investigate treatment feasibility by assessing treatment completion and withdrawal (See Specific Aim 3 below). We define the feasibility of iTBS will be defined as feasible by as completion of 15/20 (75%) iTBS treatment sessions by all subjects **AND** withdrawal from treatment of no more than one of five subjects (20%) due to intolerable side effects or persistent symptoms of

MDD. Investigation of efficacy, durability, safety as well as feasibility simultaneously is essential in this preliminary study of the use of iTBS in adolescents in order to justify a larger future study.

Non-Clinical and Clinical Study Findings

Potential Risks:

Breach of Confidentiality: Like with all research, there is an unlikely but potential risk of confidentiality being broken. Due to the stigma with mental health disorders, if someone were to discover a patient participated in this study, it is possible for them to face embarrassment or discrimination. However, all paper study files will be coded and kept in a locked cabinet, in a locked office, in a secure building at all times. The facility used is routinely used for clinical research as well as routine psychiatric care. Study staff will be the only ones with access to this information unless required by law. Additionally, study staff are trained on confidentiality guidelines for patient healthcare and as research subjects. In allowable circumstances, paper material that are allowed to be destroyed will be shredded by UNC (University of North Carolina) healthcare-grade shredding system. In addition, questionnaires will be done in a private office to protect their identity. Electronic files are stored securely on UNC-provided equipment and complies with all technological security requirements.

Risk of Embarrassment: It is possible that by answering questions during screening and throughout the study that a patient may feel uncomfortable or embarrassed to answer questions. Subjects will be answering these questions in a private office to protect their identity.

Risk of Pain or Discomfort: Some discomfort may temporarily occur during treatment. There may be mild and temporary scalp pain where treatment is administered, in all recorded instances of previous studies, this recovered without intervention and was mild in severity.

Risk of Seizure: This is a very low risk, but more likely to happen if the subject has a history of seizures or central nervous system disorders.

Current side effect statistics below:

iTBS is new for adolescents and kids. So far, however, safety data is extremely similar for that of adults. We looked at current safety data for iTBS used in anyone under 18 years old. The below information summarizes safety data.

- Mild side effects that are brief and resolve on their own without intervention (headaches, local discomfort, pain, tingling, dullness, scalp pain, nausea, loss of appetite, change in hearing, neck stiffness, finger twitching, fatigue, musculoskeletal problems) : 9-12.4 % of participants
- Moderate side effects (headaches, ringing in ears, neurocardiogenic syncope): 1.3%
- Serious side effects (seizures): 0% in kids treated with iTBS in studies performed so far. The risk for seizure increases if someone has central nervous system disorders or a history of epilepsy. In regular Transcranial Magnetic Stimulation (TMS), the risk is .06%

There is no known risk for increasing suicidality by using iTBS. In addition, patients who are imminently suicidal will not be allowed to participate in the study. Appropriate referrals will be made should this happen.

Potential Benefits:

Potential benefits include a reduction in depressive symptoms. This in turn can alleviate other impairments in functioning that are caused by depression; such as better sleep, appetite, socialization, school and work functioning, and overall wellness. This will be measured and tracked through HAM-D and CDRS-R assessments (more information on these assessments in section 5.2)

Additional Follow-up: Patients will continue to be seen by their regular provider and specialist, and may find benefit in working with an additional treatment team for closer follow-up.

Risk /Benefit Assessment

Due to the need to expand treatment for MDD and similarities between the risks and benefits to other treatment options currently available or other clinical studies, it has been determined that the potential benefits outweigh the potential risks.

1.5 Relevant Literature and Data

See section 5.2

2.0 STUDY OBJECTIVE

The purpose of the study is to determine the efficacy/durability, the safety, and the feasibility of iTBS in 5 adolescents with MDD.

Specific Aims.

Aim 1. Investigate the efficacy and durability of effects by estimating the magnitudes of pre-regimen vs. post-regimen longitudinal changes in CDRS-R, HAM-D, and NSSIB evaluations.

Hypothesis 1: Adolescents with MDD will show improvement in symptoms over 20 iTBS sessions as measured by the Children's Depression Rating Scale Revised (CDRS-R), HAM-D and NSSIB measures.

Hypothesis 2: Adolescents with MDD will show reduction of depressive symptoms will persists through the 12 week follow up period of the study.

Hypothesis 3: Adolescents with MDD who demonstrate NSSIB at the start of the trial will show reduction in NSSIB after iTBS treatments.

Aim 2. Investigate safety of the treatment regimen by assessing suicidality with the Columbia Suicide Severity Rating Scale (C-SSRS).

Hypothesis 1: Adolescents with MDD will show reduction in suicidal thoughts and behavior with iTBS treatment as measured by the Columbia Suicide Severity Rating Scale (C-SSRS) and a psychiatrist's clinical assessment.

Aim 3. Investigate treatment feasibility by assessing treatment completion and withdrawal.

Hypothesis 1: iTBS will be considered feasible if: a.) 15/20 (75%) iTBS treatment sessions are completed by all subjects, and; b.) no more than one of five subjects (20%) withdraw from iTBS due to intolerable side effects or persistent symptoms of MDD.

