3.2 Allocation to Treatment Groups and Blinding (if applicable): N/A

3.3 Study Duration, Enrollment and Number of Subjects

5 subjects are expected to enroll. The total study participation will be over the course of 16-17 weeks, including the 24 study visits. The iTBS treatment itself will last a few minutes, and additional time will be allocated for machine set-up and additional review of symptoms as needed. Once per week during the treatment phase, subjects will also have additional cognitive and safety assessments done for safety monitoring that will last approximately 1 hour.

Given that subjects will need to come in 4 consecutive weeks Monday-Friday for treatments, it is likely one patient will be treated at a time. With the need to enroll and complete all data collection within a year, minus startup time, it is feasible to enroll 5 patients. In addition, iTBS has not been used in patients younger than 16 before, and while there is no safety concern for this, it would make sense from a safety perspective to start with a smaller number of participants. The data used from this study will then be used to pursue larger grant opportunities such as R01 to enroll more subjects that will allow for statistical significance calculations.

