3.4 Study Population

Inclusion Criteria:

- A score of greater than 40 on the CDRS-R and 17 on HAM-D.
- Documentation of DSM-V criteria for current MDD or TRD will be required for study entry.
- Patients may be on antidepressant medication at a stable dose or receiving psychotherapy with a licensed provider during the active phase of TMS treatment for 4 weeks.
- Ability to provide consent and take part in questionnaires and scales (i.e.: not currently intellectually disabled).
- The presence of suicidality or NSSIB are not required to enter this study. Although our secondary endpoints include suicidality, and we are also exploring NSSIB, and thus this may not lead to many data, the investigators' plan is to use data from this study to justify a larger study where this can be more robustly investigated.

Exclusionary criteria:

- Past or current diagnosis of bipolar disorder, psychosis, seizures or traumatic brain injury.
- Presence of intracranial metallic implants or fragments, which is a contraindication for TMS.

- Lifetime history of (or currently present) epilepsy.
- Current diagnosis of substance abuse, eating disorder, PTSD (Post Traumatic Stress Disorder), or intellectual disability.* Nicotine use disorder will not directly preclude a potential subject from this study. Although chronic nicotine use does effect central nervous system excitability, [23] what would be more confounding to our study would be if there is a sudden change in nicotine use during the treatment phase, as this may affect the motor threshold. Inclusion will however be at the PI's discretion.
- Current imminent suicide ideation or other clinical reasons for inpatient psychiatric hospitalization.
- Currently pregnant. There is currently not adequate data from this population to ensure safety with the scope of this protocol.
- Any reason the investigator determines may cause noncompliance with study rules or is unfit for receiving treatment.
- Currently taking certain medications including antidepressants, stimulants, benzodiazepines, and antipsychotics, antiepileptic (see Appendix A).
- Any positive drug testing from a urine drug test unless medically indicated with a valid prescription.

*Those with marijuana/cannabis positive results may retest later if at that time they do not meet criteria for substance abuse at screening and agree to refrain from use for the duration of study participation. Decision to be made by Investigator discretion.

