5.0 STUDY EVALUATIONS AND MEASUREMENTS

5.1 Safety Evaluation

- **Variables that will be abstracted from medical charts:** General medical health and stability (current), concomitant medications, medical history, and diagnosis will be used to help determine patient eligibility.
- **Baseline evaluation:** Baseline will be done at screening while eligibility is determined. SCID-5, CDRS-R, HAM-D, MMSE, Trails B, List Generation, a semi-structured interview, and C-SSRS will be used for diagnosis of depression and baseline cognitive functioning.
 - SCID-5 – This is a structured interview to evaluate psychiatric diagnosis in children and adolescents. Interrater reliability ranges from .78-1 depending on the diagnosis. [23] This is a descriptive, yes/ no, diagnostic assessment that will only be used at screening.

- UDS and urine pregnancy tests for childbearing-capable participants will be performed at screening for eligibility purposes. Investigators will only repeat these tests as a discretionary basis if there is concern for pregnancy or unauthorized drug use that can cause the participant potential harm in conjunction with study participation.

- **How measurements will be taken:** Assessments will be done by a trained study staff in a private setting to ensure patient comfort and ability to answer questions. Various questionnaires will be used to measure baseline and efficacy, as listed above in section 5.1. These will be done at screening, and the end of each treatment week (4 times total during treatment phase), and again at each of the 3 follow-ups.

- **Rating scales, tests, psychological tools, laboratory evaluations, etc.** Assessments are described in section 5.2.

- **Safety evaluations** include vitals being monitored and a physical exam. Vitals will be monitored every visit. UDS and urine pregnancy test will be done at screening and any other time the investigator deems suspicion it is necessary for safety purposes. A physical exam will be done at screening and all follow up visits. Concomitant medication tracking and AE review will be done at every visit. Attention will also be placed on any change in medications or doses. Psychiatrists will evaluate safety through medical review of symptoms at each study visit and monitor treatment sessions. Additional questionnaires for safety and cognitive evaluation once per week during the treatment phase. Please see Appendix B for detailed information.

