- Columbia-Suicide Severity Rating Scale (C-SSRS) – C-SSRS is a tool widely used in clinical settings to assess suicidality. A large problem before the scale's existence was a lack of uniformity among assessing suicidality. C-SSRS was created to address this measuring four different constructs. These constructs are severity of ideation, intensity of ideation, behavior subscale, and lethality subscale. C-SSRS is endorsed and recommended by multiple health and mental health related organizations. C-SSRS is an effective assessment tool for clinical and research environments. [25] This is a descriptive and yes/no assessment.

- Cognitive assessments:

Mini-Mental Status Exam (MMSE): MMSE is a tool used to assess cognitive function. It consists of 30 items assessing orientation to time, orientation to place, attention and calculation, registration, recall, language, repetition, and complex commands. While used primarily for assessment of dementia in older adults, MMSE is useful in assessing and screening intellectual disabilities in children and adolescents. Preliminary studies found and concluded that MMSE could be used as a tool to assess cognitive function of children ages 4 and older. [26] This is a scored assessment.

Trail Making Test Part B (TMT-B): TMT (Trails Making Test) is another tool used to assess cognitive function. The test consists of two parts. Part A consists of connecting the dots together in sequential order based on numbers (1,2,3...). Part B consists of the same idea but uses and alternates both letters and numbers (1,A,2,B,3,C...) with the goal of connecting the dots in sequential order. TMT has a number of studies that supports its effectiveness and depicts its ability to differentiate between children with achievement deficits and learning disabilities from their normally developing peers. Trails B has been found to be more sensitive to these differences than Trails A. [27] This is a scored assessment.

List Generation: This assessment determines the ability for one to recall as many items as possible in a given category. This study will utilize “animal names”, where subjects are to recall at least 14 animals with a 60 second period. This is a scored assessment.

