6.2 Secondary Endpoint

- To evaluate the reduction of suicidality in adolescents with MDD: This will be done with descriptive and repeated measures ANOVA.
- To assess durability of antidepressant effect: This will be done with descriptive and repeated measures ANOVA.
- To evaluate the change in Non-suicidal Self Injurious Behavior (NSSIB): This will be evaluated with descriptive statistics.
- Evaluation of adverse events will be performed at every visit and documented according to GCP guidelines. Appropriate follow up and referrals will be made as needed.

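### Aim 2, the safety aim, plans to show a reduction in suicidality in all subjects and commits to no count of new or worsened suicidality, although subjects may enter with none

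*Combined protocol and SAP*

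**What the plan says.** - **Aim and hypothesis.** Section 2.0 gives Aim 2 as the safety aim, assessed through suicidality on the C-SSRS. Its single hypothesis is "Adolescents with MDD will show reduction in suicidal thoughts and behavior with iTBS treatment", measured by the C-SSRS and a psychiatrist's clinical assessment. Section 1.2 repeats this as an expectation.
- **Endpoint and analysis.** Section 6.2: "To evaluate the reduction of suicidality in adolescents with MDD: This will be done with descriptive and repeated measures ANOVA". Section 6.3 adds a Pearson correlation between C-SSRS scores and the depression scores. Its safety paragraph describes monitoring and defines no C-SSRS summary.
- **Entry.** Section 3.4: "The presence of suicidality or NSSIB are not required to enter this study". The same section warns that few data on this may result. It also excludes the severe end: "Current imminent suicide ideation or other clinical reasons for inpatient psychiatric hospitalization".
- **Scale.** Section 5.1 says of the C-SSRS: "This is a descriptive and yes/no assessment". It lists severity and intensity of ideation among the constructs, but no section defines a score to be averaged.
- **Size and schedule.** Section 3.3: "5 subjects are expected to enroll". Appendix B schedules the C-SSRS at screening, at the end of each of the four treatment weeks (V6, V11, V16, V21) and at three follow-ups (V22 to V24).
- **Other safety capture.** Adverse events are reviewed at every visit and appear in the same section 6.2 list. The Appendix C log takes separate entries for new events, increased severity and worsened pre-existing conditions.

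**The concern.** A safety aim should show harm if harm occurs. This one is written in the direction of benefit and applied to everyone, including subjects who cannot show that benefit. For an adolescent with no suicidality at screening, the only change the scale can record is an increase, which is the event a safety aim exists to find. A repeated measures ANOVA compares visit means, so that increase is netted against decreases in others.

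Two uninformative results become possible. The group can show a lower mean while one adolescent has new ideation, or it can show no reduction because most subjects had nothing to reduce. This matters beyond five subjects: section 6.4 intends the data to support larger grant applications, and section 3.3 states that iTBS has not been used below age 16.

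**Working it through.** The plan gives no alpha, power, effect size or event rate for suicidality, and five subjects were chosen largely on practical grounds, so there is no figure to reproduce. The inputs from the documents are N = 5, no suicidality required at entry, and 8 scheduled C-SSRS ratings (1 at screening, then 4 + 3 = 7). Everything marked as assumed is not in the documents.

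**1. Floor.** A subject at zero can stay at zero or rise. This follows from section 3.4 and needs no assumed figure. To see how often it matters, let q be the assumed share of eligible adolescents with suicidality at screening. The chance that at least 3 of 5 start at the floor is the sum over k = 0, 1, 2 of C(5,k) q^k (1-q)^(5-k).
- For q = 20%, 40%, 60%, 80%: 94%, 68%, 32%, 6%.
- The chance that all five start at the floor, (1-q)^5: 33%, 8%, 1%, 0.03%. A reduction is then impossible.

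**2. Offsetting, on an assumed 0-5 ideation severity score (illustration only).**
- Screening 3, 3, 0, 0, 0 has mean 6/5 = 1.2. End of treatment 1, 1, 0, 0, 3 has mean 5/5 = 1.0. The mean change is -0.2 (paired p = 0.84), while 1 of 5 subjects (20%), or 1 of the 3 without ideation at screening (33%), has new ideation at level 3.
- In general, if k subjects each fall 2 points and one floor subject rises to r, the mean change is (r - 2k)/5. It is negative whenever r < 2k: up to r = 1 for k = 1, up to r = 3 for k = 2, and any r up to 5 for k = 3 or 4.
- Over 8 visits, take subjects at 3,3,2,2,1,1,1,1; 3,2,2,1,1,1,1,1; two at zero throughout; and one at zero except for a 3 at the last treatment week. The visit means are 1.2, 1.0, 0.8, 0.6, 1.0, 0.4, 0.4, 0.4, with F(7,28) = 1.04 and p = 0.43. Every later mean is below screening.

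**3. The same data read as yes/no.** The first example goes from 2/5 with ideation to 3/5, so the new case is visible. If instead the two positive subjects resolve fully (3, 3, 0, 0, 0 to 0, 0, 0, 0, 4), the proportion falls from 2/5 to 1/5 and the mean from 1.2 to 0.8, again with one new case. Netting is therefore possible on either reading, but not in every data set.

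**4. A per-subject count.** Exact (Clopper-Pearson) 95% intervals at N = 5:
- 0/5: 0% to 52.2%, the upper limit being 1 - 0.025^(1/5)
- 1/5: 0.5% to 71.6%
- 2/5: 5.3% to 85.3%

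The chance of seeing at least one case, 1 - (1-p)^5, is 23%, 41%, 67% or 83% for an assumed true risk of 5%, 10%, 20% or 30%.

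**The case against.** A reader might infer that the plan declares the treatment safe when the mean C-SSRS falls. The documents do not say that. Section 1.2 presents the reduction as an expectation, and only Aim 3 carries a decision criterion. Safety also rests on cognitive tests, the NSSIB interview, medical review and adverse events.

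A reader might also infer that new suicidality would go unseen. That is not supported either. Descriptive statistics and a psychiatrist's assessment are part of the planned readout, the C-SSRS is given weekly during treatment, and the adverse event log works subject by subject. The section 2.0 contrast with NSSIB is weaker than it looks: Aim 1 Hypothesis 3 is limited to those with NSSIB at the start, but Aim 1 Hypothesis 1 expects improvement on it in all subjects.

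The numerical illustration needs a score that the plan does not define. Section 6.4 also requires confidence intervals with all estimates. For changes of -2, -2, 0, 0, +3 the 95% t interval is about -2.7 to +2.3, which no careful reader would call a reduction. The sparse data are disclosed in section 3.4.

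All of this stands, and it limits the point to the Aim 2 hypothesis and its analysis. It does not remove the point. No section commits to a per-subject listing, defines worsening, or brings a new case into the Aim 2 result. The disclosure concerns few data, not the offsetting of harm.

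**Conclusion.** The point holds for the Aim 2 hypothesis and the section 6.2 suicidality endpoint, not for safety monitoring as a whole. The floor follows from the entry criteria alone. The offsetting is a property of comparing visit means: a new case can be averaged away, but need not be. Its size depends on an assumed 0-5 score and assumed shares. With 20% to 80% of subjects having suicidality at screening, the chance that at least three of five start at the floor runs from 94% down to 6%.

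Visit means by ANOVA are a poor fit to a scale that the plan calls yes/no, in five subjects who may start at zero. A count is better suited, although it cannot prove safety at this size. The change is worth making before analysis; the point does not invalidate the study.

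**What to change.** In section 2.0 (Aim 2) and section 6.2:
- Make the safety readout the number of subjects with any new or worsened C-SSRS ideation category, or any new suicidal behaviour, against their own screening rating, at any of the seven later ratings (V6, V11, V16, V21, V22 to V24). List it by subject and give an exact 95% confidence interval. State that 0/5 would not establish safety.
- Report reduction only among subjects with suicidality at screening, and state that denominator.
- Do not use the repeated measures ANOVA of the C-SSRS as the safety result.

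The cost is wording in two sections and one small table from ratings already scheduled, with no added visits or assessments. The downside is a smaller denominator for the reduction claim, which could be zero.
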